#### J. VACCINE EXPOSURE

TIV will be initially identified in claims-based data using NDC (National Drug Codes), CPT (Current Procedural Terminology), HCPCS (Healthcare Common Procedure Coding System) and ICD9 (International Statistical Classification of Diseases) codes (Appendix 6). These include codes used by healthcare providers and insurers prior to the 2012-13 influenza season for capturing seasonal inactivated influenza vaccines for administrative and reimbursement purposes. TIV exposure will also be identified in IIS data (i.e., immunization registries, maintained by Departments of Health) using CVX (Vaccines administered) codes. We will conduct chart review to verify vaccine exposures.

#### K. CASE-TIME-CONTROL DESIGN

As proof-of-concept, a case-time-control study design will be implemented to examine whether risk of SAB is elevated in specific time periods following TIV or in specific gestational periods following TIV. We will identify SAB cases that were vaccinated between -4 weeks gestation until the date of the SAB. Since the likelihood of receiving TIV differs by gestational age and calendar time, we will match each case to a vaccinated control based on Data Partner, maternal age, and pregnancy start, where the control must have received TIV between -4 weeks gestation and the case's gestational age at SAB. In order to understand the feasibility of using the case-time-control design in Mini-Sentinel, we will first examine (1) the validity of claims data for identifying SAB; (2) the validity of birth certificate and claims data for identifying start among live delivery controls for matching them to chart-confirmed cases; and (3) the validity of using claims data for matching cases to controls on confounders, if matching on factors other than DP and pregnancy start is ultimately implemented. The details of the descriptive statistics for Primary Objectives 1-3, which will be used to address each of these aims, are described further in the analytic section of the protocol.

In Pilot Objectives 4-5, we will implement the case-time-control design and analyze the resulting data. For Pilot Objective 4, we will define the risk interval as receipt of TIV within 1-28 days prior to SAB, while the control interval will be defined as receipt of TIV outside of the risk interval (i.e., between -4 weeks gestation and 29 days prior to SAB, Figure 2). Although we will strive for an exact match by pregnancy start, it is plausible that we will not identify enough controls to match to cases. If an exact pregnancy start match is not possible, we will assign an index date in controls that corresponds to the gestational age at SAB in the case. Of note, cases and controls will only be informative if vaccinated in either the risk or the control interval. In exploratory analysis, we will stratify the analysis for this objective by gestational age at SAB (less than 12 weeks gestation vs. 12 or more weeks gestation) since the etiology of SAB differs by gestational age at occurrence. In addition, because the underlying causes of SAB may differ by whether a heartbeat is detected prior to the miscarriage, we will consider stratifying by this factor, depending on whether we have sufficient case numbers. If we have sufficient case numbers, we will also consider excluding cases that have a threatened abortion identified prior to vaccination.

**Figure 2:** Example case and control for case-time-control design with the risk interval defined as 1-28 days before SAB, and the control interval design defined as -4 weeks gestation through 29 days before SAB. Follow-up time after the SAB and index dates will be censored.

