#### B. ANALYTIC PLAN FOR CASE-TIME-CONTROL DESIGN (PILOT OBJECTIVES 4-5)

For the case-time-control design, conditional logistic regression stratified by case:control set will be conducted. The use of conditional logistic regression, in contrast to standard logistic regression, will allow each matched case:control set to have a different odds ratio for time trend in exposure without specifying its function in the model. The outcome will be the probability that an individual's vaccination occurred in the risk interval (1=yes, vaccinated in risk interval; 0=no, vaccinated in control interval); the independent variable will be case vs. control status (1=case; 0=control), with the corresponding coefficient estimating the final odds ratio estimate, adjusted for time trend in exposure. Where

applicable, we will also adjust for time-varying confounders not matched upon by including terms in the model.

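### The optional threatened-abortion exclusion selects cases on when they were vaccinated but sets no matching cut-off for controls, which biases that analysis's 1-28 day odds ratio downward

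*Protocol*

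**What the plan says.** Protocol section III.K sets up Pilot Objective 4. On the risk interval it says "we will define the risk interval as receipt of TIV within 1-28 days prior to SAB"; the control interval is TIV received "between -4 weeks gestation and 29 days prior to SAB". Eligibility of controls runs to the same end point as for cases: "the control must have received TIV between -4 weeks gestation and the case's gestational age at SAB". If pregnancy start is not matched exactly, "we will assign an index date in controls that corresponds to the gestational age at SAB in the case". Both control rules are anchored to the SAB, and neither refers to a threatened abortion.

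Among the exploratory variants of this objective, and subject to sufficient case numbers, the same section adds: "we will also consider excluding cases that have a threatened abortion identified prior to vaccination". It does not say what happens to the matched controls. The version 3 entry in the History of Modifications speaks of removing them with the cases, and I assume that here.

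Section IV.B gives the model: "conditional logistic regression stratified by case:control set will be conducted". On the response it says "The outcome will be the probability that an individual's vaccination occurred in the risk interval", and on the predictor, "the independent variable will be case vs. control status (1=case; 0=control". Section III.I leaves one control per case, chosen at random when two qualify.

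**The concern.** The model's response is whether vaccination fell in the risk interval. The exclusion depends on the order of vaccination and threatened abortion, so it selects cases on that response.

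Take two cases whose threatened abortion was recorded 14 days before the SAB. The one vaccinated before the record stays. The one vaccinated after it goes, and she was necessarily vaccinated within 14 days of the SAB, so inside the risk interval. Her matched control leaves with her but was not chosen for its own vaccination time. The remaining controls therefore keep their full proportion in the risk interval, while the remaining cases have lost part of theirs.

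The likely aim, although the protocol does not state it, is to set aside vaccinations that came after the loss had begun. As written, the rule builds in an odds ratio below 1 when the vaccine has no effect. A reader who compared this analysis with the main one could take a fall in the odds ratio as reassurance when part of the fall comes from the rule.

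**Working it through.** The protocol states no figure for this exclusion, so there is none to reproduce. The check is the odds ratio expected when vaccination has no effect.

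**Inputs from the protocol**
- Risk interval: 28 days (III.K).
- Exposure window: from -4 weeks to the SAB. With SAB at 10 weeks, the average given in III.F, this is 14 weeks = 98 days.
- 1:1 pairs (III.I), so the conditional odds ratio is n10/n01. Here n10 counts pairs with only the case in the risk interval and n01 pairs with only the control in it.

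**Assumptions not in the protocol**
- f: share of cases with a recorded threatened abortion.
- L: days from that record to the SAB.
- Vaccination timing uniform over the window and the same in cases and controls.

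**Closed form, L up to 28 days**
- Without exclusion: p0 = 28/98 = 0.286 in both groups, and OR = 1.
- Share of cases excluded: e = f x L/98, all of them in the risk interval.
- n10 is proportional to (p0 - e)(1 - p0), and n01 to (1 - p0)p0.
- OR = (p0 - e)/p0 = 1 - f x L/28. The window length cancels, so gestational age at SAB does not matter.

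| f | L = 7 | L = 14 | L = 21 | L = 28 |
|---|---|---|---|---|
| 10% | 0.975 | 0.95 | 0.925 | 0.90 |
| 20% | 0.95 | 0.90 | 0.85 | 0.80 |
| 30% | 0.925 | 0.85 | 0.775 | 0.70 |
| 40% | 0.90 | 0.80 | 0.70 | 0.60 |

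**L above 28 days.** Some control-interval cases go as well, but all risk-interval vaccinations of these women go. At 10 weeks, OR = (1 - f)/(1 - f x (L - 28)/70). For f = 25% and L = 35 this is 0.75/0.975 = 0.77, still below 1.

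**Pair counts per 100 starting pairs, f = 30%, L = 14**
- As written: removed 100 x 0.30 x 14/98 = 4.3; n10 = 100 x (0.2857 - 0.0429) x 0.7143 = 17.3; n01 = 100 x 0.7143 x 0.2857 = 20.4; OR = 0.85.
- Both members cut at the threatened abortion: removed 100 x 0.30 x (1 - (84/98)^2) = 8.0; n10 = n01 = 100 x [0.70 x 0.2041 + 0.30 x (14/98) x (70/98)] = 17.3; OR = 1.
- All threatened-abortion sets dropped: removed 30; OR = 1.

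**Simulation.** One million null pairs were drawn per scenario, with gestational age at SAB varying around 10 weeks, exponential lags with mean 7, 14 or 21 days, and vaccination timing either uniform or rising with gestational age. The odds ratio was 0.99-1.01 without exclusion. Under the written rule it was about 0.95-0.98 (f = 10%), 0.88-0.94 (25%) and 0.75-0.88 (50%). With the two-sided cut, or with all threatened-abortion sets dropped, it was 0.99-1.01.

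**If a threatened abortion changes later vaccination** (f = 25%, L = 14, later rate multiplied by 0.5, 1 or 2): without exclusion the odds ratio is 0.94, 1.00 or 1.125. With the written exclusion it is 0.875 each time, because every vaccination after the threatened abortion is removed from the cases.

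**The case against.** The strongest reply concerns weight. The analysis is exploratory, depends on case numbers, and is only to be considered. The main Objective 4 estimate is not touched. All of that stands.

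The size is not known either. The protocol gives no frequency of threatened abortion and no lag. The rule refers to a threatened abortion that was identified, which may be rarer than bleeding, and section III.O says that symptom onset is variably captured in records. If f is 10% or less and the lag is short, the bias is a few percent. In a study of 100 pairs it would also be lost in the noise: at f = 25% and a mean lag of 14 days, n10 is 18.2 and n01 is 20.4, so the standard error of the log odds ratio is sqrt(1/18.2 + 1/20.4) = 0.32, against a shift of log 0.89 = -0.12. This stands as well.

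It can also be said that where threatened abortion prompts more vaccination, the main analysis errs upward (1.125) and this one downward (0.875), so the two bracket the truth. That is so in that scenario. With no change in later vaccination, the main analysis is unbiased and only the exclusion introduces an error.

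A statistical analysis plan might settle what happens to the matched controls. That would not help: removing the control with its case still leaves the selection one-sided.

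A reader might infer that a real increase would disappear in this analysis. The documents do not support that. If the null factor is carried over to a true effect, the detectable relative risk of 2.4 in section V.B (stated there for the 2-6 week interval) becomes 2.4 x 0.95 = 2.28, 2.4 x 0.85 = 2.04 or 2.4 x 0.70 = 1.68. It shrinks but remains well above 1.

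**Conclusion.** The point holds for this one optional analysis. The exclusion is defined on exposure timing in cases with no counterpart in controls, so its 1-28 day odds ratio is biased downward. The direction does not depend on uniform timing, on gestational age at SAB, or on whether threatened abortion alters later vaccination. It needs only that some cases were vaccinated between a recorded threatened abortion and the SAB.

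The size cannot be fixed from the protocol and ranges from negligible to moderate with f and the lag. What is at risk is the reading of a modest increase, which could look smaller here than in the main analysis because of the rule alone. It should not be read as a flaw in the main Objective 4 result. This is a stated rule that gives a biased answer, not a detail left for later, and it is worth correcting because the study is meant to inform the methods of later pregnancy surveillance.

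**What to change.** Replace the exclusion in section III.K with a rule for the pair. For a case with a recorded threatened abortion, end the eligible exposure window of both the case and her matched control at the gestational age when the threatened abortion was identified, and keep the pair only if both were vaccinated before that point. The risk and control intervals can stay anchored to the SAB or index date.

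Cost: at f = 30% and a 14-day lag, about 8 rather than 4 of 100 pairs leave this sensitivity analysis. The standard error of the log odds ratio goes from sqrt(1/17.3 + 1/20.4) = 0.33 to sqrt(2/17.3) = 0.34. The date of identification is needed, but the present rule already needs it to order the two events.

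Dropping every set whose case had a threatened abortion also restores a null odds ratio of 1, but it is not preferred. It loses about 30 of 100 pairs at f = 30%, and it removes women vaccinated before the threatened abortion, in whom it could be an early sign of the outcome under study.

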**PRISM Surveillance Protocol** 

Influenza Vaccines And Pregnancy Outcomes **Figure 5:** Example case and control for case-time-control design with the risk interval defined as 6 to 11 weeks gestation, and the control intervals defined as the combined period of -4 through 5 weeks and 12 weeks gestation through the case's gestational age at SAB. Follow-up time after the SAB and index dates will be censored.

L. TEMPORAL SCAN, TIME DEFINED AS DAYS PRIOR TO SAB (PILOT OBJECTIVE 6)

In the Pilot Objectives 6-8, we will use the study population from Pilot Objectives 4-5 to examine whether risk of SAB is elevated during potential periods of increased risk without defining them a priori. Specifically in Pilot Objective 6, potential risk intervals will be defined by the number of days prior to SAB that TIV was received. We will search among cases for potential clusters of TIV within a period of 1-90 days prior to SAB event, adjusting for timing of vaccination in matched controls (Figure 6). Window lengths may range between 1 and 14 days and start and end within the period defined in the primary analysis (i.e., -4 through 20 weeks gestation). The timing of TIV in maternal age and pregnancy start-matched controls will be used to adjust for temporal clusters in cases arising from seasonal and gestational age patterns.

**Figure 6**: Hypothetical data for temporal scan with timing of TIV defined by number of days prior to SAB; the X's represent the timing of TIV before SAB in cases. The timing of TIV in maternal age and pregnancy start-matched controls is used to adjust for temporal patterns by gestational age and calendar time.

#### Cases

#### M. TEMPORAL SCAN, TIME DEFINED AS GESTATIONAL AGE (PILOT OBJECTIVE 7)

For Pilot Objective 7, we will examine whether there may be a susceptible gestational age when exposure to TIV increases the risk of SAB without defining the gestational period a priori. We will use the same case and control set as in Pilot Objectives 4-5. Since the likelihood of receipt of TIV differs by gestational age and calendar time, we will use the same group of live delivery controls from the first aim, which have been matched to controls on maternal age and pregnancy start. Among cases, we will search for potential clusters of TIV within a study period of -4 through 20 weeks gestation (Figure 7). We will use windows that may range in length between 1 to 4 weeks. The timing of TIV in age and pregnancy start-matched controls will be used to adjust for temporal clusters in cases arising from seasonal and gestational age patterns in vaccination.

**Figure 7:** Hypothetical data for temporal scan with timing of TIV defined by gestational age at receipt; each x represents the timing of TIV before SAB in a case. The timing of vaccination in age and pregnancy start-matched controls is used to adjust for temporal patterns by gestational age and calendar time.

# N. TEMPORAL SCAN, TIME DEFINED BY NUMBER OF DAYS PRIOR TO SAB AND GESTATIONAL AGE (PILOT OBJECTIVE 8)

We hypothesize that the risk of SAB, if related to vaccination, may be dependent both on time since vaccination and on gestational age at vaccination. In order to explore whether it is a combination of these time scales that contribute to the risk of SAB among women receiving TIV, we propose to conduct a 2-dimensional temporal scan. In the cases and controls described previously for Pilot Objectives 4-5, we will use both the information collected on number of days prior to SAB and on gestational age at

receipt of TIV. We will then search for potential temporal clusters of vaccination, where time is defined in a 2-dimensional space by gestational age at TIV receipt and by number of days TIV received prior to SAB event. Clusters may occur anywhere between 1-90 days prior to SAB events, provided that they occur between -4 to 20 weeks gestation (Figure 8). We will consider longer study periods when defining days prior to SAB in sensitivity analyses. The length of the windows for days prior to SAB may range between 7 and 14 days, inclusive, while the length of the windows for gestational age at vaccination may range between 1 and 4 weeks, inclusive. The length of one dimension will not influence the length of the other dimension. The timing of TIV in pregnancy start-matched controls will be used to adjust for temporal clusters in timing of TIV in cases due to gestational age and seasonality of vaccination.

**Figure 8:** Hypothetical data for two-dimensional temporal scan; each x represents the timing of vaccination with respect to gestational age (x-axis) and days prior to SAB event (y-axis) in a case. The timing of vaccination in age and pregnancy start-matched controls is used to adjust for temporal patterns in vaccination by gestational age and calendar time.

#### O. MEDICAL RECORD REVIEW OF SAB CASES AND LIVE DELIVERY CONTROLS

All SAB cases will be adjudicated by an obstetrician or other physician (e.g., family physician) with experience in providing obstetric care to confirm SAB and estimate the dates of SAB and pregnancy start. SAB cases will be considered to be confirmed if intrauterine pregnancy (via, ultrasound or other clinician documentation) and natural pregnancy loss prior to 20 weeks gestation is documented in the medical record. For a sensitivity analysis, we will consider collecting information on the presence of congenital anomalies that may affect fetus viability from the medical record, to be excluded both among cases and controls. We will also consider conducting another sensitivity analysis that excludes cases with medical record documentation of a blighted ovum (also called an embryonic gestation), and their

matched controls, if numbers permit. In addition, information on potential risk factors for SAB, including asthma, gravidity, prior history of SAB, diabetes, febrile illness, medically attended infections, and obesity, will be collected primarily for descriptive purposes. If feasible, we will adjust for smoking, alcohol, and substance abuse in regression models, using information from the medical record.

All SAB events estimated to have occurred prior to 6 weeks gestation will be excluded since recognition of pregnancy loss prior to this point is uncommon and thus it is difficult to establish date of pregnancy start and date of SAB. Potential cases or controls for whom it is determined that TIV did not occur between -4 weeks gestation and the case's gestational age at SAB event (i.e., the study period of interest) will also be excluded.

Accurate assessment of SAB date and gestational age is necessary for determining timing of vaccination in relation to SAB date/index date in controls and gestational age at vaccination, both of which define potential risk intervals in this study. Medical records will be used to assign date of SAB among cases and estimated pregnancy start among cases and controls. The American College of Obstetrics and Gynecologists (ACOG) currently includes the following indications for an ultrasound during first trimester (before 13 weeks and 6 days gestation), among others: confirmation of an intrauterine pregnancy, evaluation of a suspected ectopic or molar pregnancy, evaluation of vaginal bleeding or pelvic pain, estimation of gestational age, and confirmation of cardiac activity. Among other indications, second and third trimester ultrasound is indicated for estimation of gestational age, evaluation of fetal growth, vaginal bleeding, or abdominal/pelvic pain, or evaluation of suspected fetal death, molar pregnancy, or ectopic pregnancy. Of note, ACOG recommends to use caution when estimating gestational age using third trimester ultrasound because its accuracy is only within 3-4 weeks.

We will use the date of SAB diagnosis for assigning number of days of the case event relative to vaccination and gestational age of the case event. While we considered incorporating ultrasound fetal dating and symptom onset, they have several limitations. First, there is variable capture of this information in medical records. Second, ultrasound fetal dating may be inaccurate, due to restricted fetal growth in pregnancies ending in early pregnancy loss; furthermore, symptom onset may not accurately reflect onset of a miscarriage because symptoms of a normal pregnancy may overlap with that of an occurrence of a pregnancy loss. Third, related to the second point, it would likely be difficult to obtain inter-rater reliability because of the inherent challenges in capturing clinical intuition into a standard, replicable algorithm.

Among confirmed SAB cases, we will estimate pregnancy start using the date of procedure and embryo transfer (if applicable) in pregnancies conceived using in-vitro-fertilization or intrauterine insemination. Among naturally conceived pregnancies that end in miscarriage, we will use the date of the last menstrual period (LMP) to estimate pregnancy start.

Among livebirth controls, we will estimate date of pregnancy start using first or second trimester ultrasound or LMP in naturally conceived pregnancies and using date of the procedure or embryo transfer in pregnancies conceived using in-vitro-fertilization or intrauterine insemination. If ultrasound dating and LMP date are both available for naturally conceived pregnancies, we will use the LMP if the discrepancy between the expected due dates is seven days or less for first trimester ultrasounds or ten days or less for second trimester ultrasounds. If more than one ultrasound is available, we will use the earliest performed. If numbers permit, we will also consider conducting a sensitivity analysis restricted to matched case and control sets where LMP was used to estimate pregnancy start.

**PRISM Surveillance Protocol** 

## IV. ANALYSIS

#### A. ANALYSIS FOR PRIMARY OBJECTIVES (OBJECTIVES 1-3)

In Primary Objective 1, we will determine the feasibility of using claims data to identify potential cases for the proposed study. We will examine the positive predictive value of claims codes for SAB, using chart review as the "gold standard". We will estimate the positive predictive value (i.e., chart confirmed SAB cases divided by all potential SAB cases identified via claims data) overall, by maternal age group (18-24, 25-29, 30-34, and 35-39 years), and by claims codes (i.e., specific ICD9 or CPT code).

In addition to validating case status in Primary Objective 1, we will estimate the proportion of cases that need to be discarded because vaccination occurs prior to the period of interest (i.e., prior to -4 weeks gestation). We will also identify the optimal look-back period for vaccine codes in relation to SAB codes in electronic data to minimize the number of cases that need to be discarded because vaccination occurred before -4 weeks gestation. To accomplish this, we will tabulate the proportion of excluded cases due to this reason by days between vaccine and SAB codes in electronic data.

In Primary Objective 2, we will examine the accuracy of gestational age data in claims and in birth certificate data for the purposes of identifying pregnancy start among live delivery controls, who will be matched to chart-confirmed cases. We will estimate the proportion of controls that must be discarded because their chart-confirmed pregnancy start date is not within the pre-specified number of days from the case date. We will estimate the proportion of controls that must be discarded because their vaccination is determined via chart review to occur after the case's gestational age at SAB. We will also examine whether the proportion of discarded controls due to each of these two reasons differs by whether birth certificates or claims data were used to estimate pregnancy start date in electronic data. Finally, we will describe the distribution of matched case-control pairs by difference in pregnancy start date in cases and controls. We will stratify by whether birth certificates or claims data were used to estimate gestational age.

In Primary Objective 3, we will determine the accuracy of claims data for matching potential cases and controls on potential confounders. We will determine the positive predictive value in cases and controls for each of the confounders matched upon. We will also determine the proportion of matched case-control pairs that have concordant status in chart data for each matching factor (i.e., confounder).

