#### A. PRIMARY OBJECTIVES

- 1. To examine the positive predictive value of computerized CPT or ICD9 codes for SAB through medical record review for all cases combined and by maternal age and by code
- 2. To examine the accuracy of gestational age data in claims and in birth certificate data for the purposes of identifying pregnancy start among live delivery controls, who will be matched to chart-confirmed SAB cases

3. To examine the accuracy of potential confounders in claims data for the purposes of matching SAB cases and live delivery controls

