#### D. STUDY POPULATION

The participating Data Partners in this protocol are Aetna and HealthCore. The dates of data availability differ by Data Partner (Table 1). The study population will consist of females ages 18 through 34 years who received TIV in the 4 weeks prior to or during pregnancy, and whose pregnancies have ended in an SAB (cases) or live delivery (controls). Women whose pregnancies have ended in a therapeutic abortion, ectopic or molar pregnancy, or stillbirth will not be used as controls since we will not be able to accurately assess gestational age using claims-based data. The study population will be further restricted to women with continuous enrollment from 90 days prior to pregnancy start through the SAB date in cases or index date in controls. Though we do not anticipate this to occur frequently, cases and controls who receive an additional influenza vaccine in the 90 days prior to the start of the study period of interest (i.e., -4 weeks gestation) will be excluded.

Data Partner	Date Data Available in Mini- Sentinel Common Data Model	Requirements for Data Used in Protocol 
Data Partner A	1/1/2008 through 10/31/2012	Vaccinations occurring in 2008-09 and 2010-11 influenza seasons
Data Partner B	1/1/2004 through 11/30/2011	Vaccinations occurring in 2008-09 and 2010-11 influenza seasons

Table 1: Dates of Data Availability by Data Partner

Influenza season defined as September 1 through April 30 of the following year. 2009-10 influenza season not included due to the availability of H1N1 influenza vaccine in the same season.

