#### E. OVERVIEW OF SELECTION OF CASES AND CONTROLS

Vaccinated cases (SAB) and controls (deliveries) for this protocol will be selected in a 4-phase process (Figure 1), with a targeted final sample of 100 cases, with each case matched to at least 1 control in the final analysis. In phase 1, 140 potential cases will be initially identified in claims-based and administrative data. Also in phase 1, the initial step of identifying deliveries and estimating their pregnancy start will occur using claims-based and administrative data. If more than 140 potential cases are identified in electronic data, we will randomly sample 70 cases from each Data Partner. In phase 2, chart review will be conducted on potential cases to confirm SAB, date of SAB, and obtain pregnancy start date; potential cases will only be retained if vaccination occurred during the gestational period of interest (-4 weeks gestation to SAB event date). In phase 3, for each chart-confirmed case, we will identify 2 potential controls with the same age, pregnancy start, and vaccination between -6 weeks gestation and 2 weeks past the case's gestational age at SAB, based upon electronic data. We will randomly sample a minimum of 2 controls for each case. In the final phase, we will chart review potential controls to confirm pregnancy start, vaccination, and gestational age at vaccination.

Mini-Sentinel

Figure 1: Case and control selection for PRISM Influenza Vaccines and Pregnancy Outcomes Assessment

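### Once more than 140 potential cases are found, equal samples of 70 per Data Partner feed a PPV with no stated weights, so the overall figure matches its stated denominator only if the partners have equal case counts or equal PPVs

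*Protocol*

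**What the plan says.** Section II.A of the protocol sets the PPV of the SAB codes as the first primary objective, to be reported "for all cases combined and by maternal age and by code". Section IV.A gives the estimator as "chart confirmed SAB cases divided by all potential SAB cases identified via claims data" and lists the same breakdowns: overall, by maternal age group and by code. Neither section mentions a PPV for each Data Partner, a sampling weight or a confidence interval method.

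Section III.D names two participating Data Partners. Section III.E then fixes how many charts are pursued: "In phase 1, 140 potential cases will be initially identified in claims-based and administrative data", and "If more than 140 potential cases are identified in electronic data, we will randomly sample 70 cases from each Data Partner". The number taken from a partner therefore does not depend on how many potential cases that partner has. The protocol gives no expected count of potential cases for either partner.

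**The concern.** The two rules do not fit together once the cap is reached. The denominator in IV.A is every potential SAB case found in claims, but the charts come from a fixed 70 per partner. If one partner has more potential cases than the other, its cases have a smaller chance of being sampled. A simple ratio over the reviewed charts then gives the smaller partner more influence than its share of potential cases warrants.

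This is the first primary objective. Section II says the overarching goal is to optimize claims and birth certificate algorithms, and section V.B says the work should inform later Mini-Sentinel studies, so the PPV is a figure others may reuse. Without a breakdown by partner, a difference in code performance between the two sources would also go unreported, although it bears on feasibility.

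**Working it through.** **Inputs from the protocol.** Two Data Partners (III.D); 70 sampled from each if more than 140 potential cases are identified (III.E); PPV as confirmed cases over all potential cases (IV.A). The plan's own figure reproduces: 2 × 70 = 140. The protocol states no expected PPV and no precision target for Objective 1, so nothing else can be reproduced.

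**Inputs that must be assumed.** Partner A's share *w* of all potential cases, and the two PPVs.

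**Overall PPV when the cap applies**, with equal numbers of charts reviewed from each partner:

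- Pooled ratio = (PPV_A + PPV_B) / 2
- PPV among all potential cases = *w* × PPV_A + (1 − *w*) × PPV_B
- Pooled minus true = (0.5 − *w*) × (PPV_A − PPV_B)

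The difference is zero if *w* = 0.5 or the PPVs are equal. Results for two assumed PPV pairs, both with a pooled value of 80%:

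| Share *w* of A | True PPV, 85% / 75% | Pooled minus true | True PPV, 90% / 70% | Pooled minus true |
|---|---|---|---|---|
| 0.6 | 81% | −1 | 82% | −2 |
| 0.7 | 82% | −2 | 84% | −4 |
| 0.8 | 83% | −3 | 86% | −6 |
| 0.9 | 84% | −4 | 88% | −8 |

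Here the larger partner has the higher PPV. If it has the lower one, the signs reverse and the sizes stay the same.

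The smaller partner can supply 70 cases only if the total is at least 70 / (1 − *w*): 175 at 0.6, 234 at 0.7, 350 at 0.8 and 700 at 0.9. The larger errors therefore need a large pool of potential cases.

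**Comparison with sampling error.** The 95% half-width at n = 140 is 1.96 × √(p(1 − p)/140): 7.6 points at p = 0.7, 6.6 at 0.8 and 5.0 at 0.9. The error runs from minor to about the size of the sampling error. It would not shrink with more charts under the same equal allocation.

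**Age-group and code-specific PPVs.** These ratios also carry no stated weights, but they are not simple averages of the two partners. The mix in each subgroup follows the number of sampled cases that each partner contributes to it, so the table does not apply to them directly.

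**Precision of a weighted estimate at an 80:20 split**, 70 charts each, no finite-population correction:

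- Equal PPVs: variance ratio = [(0.64 + 0.04)/70] / [1/140] = 1.36, so the standard error (SE) is √1.36 = 1.17 times as large.
- PPVs of 90% and 70%, pooled: 1.96 × 0.5 × √[(0.09 + 0.21)/70] = 6.4 points.
- Weighted, larger partner at 90%: 1.96 × √[(0.64 × 0.09 + 0.04 × 0.21)/70] = 6.0 points.
- Weighted, larger partner at 70%: 1.96 × √[(0.64 × 0.21 + 0.04 × 0.09)/70] = 8.7 points.

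**The case against.** The best defence is that IV.A defines the quantity to be estimated, not the arithmetic for a stratified sample. A weighted estimate would target exactly that quantity, and weights may be set out in a statistical analysis plan that is not at hand. This stands in part. The protocol never says the PPV will be unweighted; that is inferred from a plain ratio with no weights. Still, the protocol itself fixes the equal allocation, the ratio and the list of breakdowns, and following all three as written does not give the stated quantity once the cap applies.

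A second defence is that IV.A presents Objective 1 as a question of feasibility for the proposed study, which is itself sampled 70 and 70. For the yield of that study the simple ratio is the relevant number. That is fair, but the stated denominator is wider, and section V.B also points to use in later studies.

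A reader might infer from Table 1 that the partners differ because their data years differ ("1/1/2008 through 10/31/2012" and "1/1/2004 through 11/30/2011"). The protocol does not support this. The same table limits both partners to vaccinations in the 2008-09 and 2010-11 seasons, and both use the Appendix 2 code list. The availability dates also cover the case window. Partner A's data start leaves the 244-day look-back complete from 1 September 2008. The 182-day window after a vaccination on 30 April 2011 ends on 29 October 2011, before Partner B's data end. A difference in coding or code mix between the partners is possible but not documented.

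**Conclusion.** The point holds conditionally and is of low severity. If more than 140 potential cases are identified, the ratio as written gives the two partners equal weight in the overall PPV, given equal chart retrieval. It then differs from the PPV among all potential cases unless the partners have equal numbers of potential cases or equal PPVs. Equal numbers here means vaccinated, enrolled, code-positive cases, not equal plan membership. With 140 or fewer, every potential case goes to chart review and there is nothing to correct.

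The size of 1 to 8 points rests wholly on assumed shares of 0.6 to 0.9 and assumed PPV gaps of 10 to 20 points. A reader might infer that the reported PPV will be biased. The protocol does not support that: it shows neither that the cap will be reached nor that the partners differ in count or PPV.

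**What to change.** In section IV.A, for the situation in which the 140 cap applies:

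- Record each partner's phase 1 count of potential cases.
- Report the PPV for each Data Partner.
- Weight the overall, age-group and code-specific PPVs, giving each reviewed chart the weight (potential cases in the partner / charts reviewed from that partner), with a stratified confidence interval. The divisor should be charts reviewed, because section V.B expects that fewer charts may be obtained than planned. This treats unobtained charts within a partner as similar to those obtained.

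This costs a few sentences and one weight per partner. It needs no extra charts and no change to the sampling or the pilot analyses. Precision changes in a direction that depends on which partner is larger. At an 80:20 split the SE is about 17% larger if the PPVs are equal, a case with no bias to remove. With PPVs of 90% and 70%, the half-width moves from 6.4 points to 6.0 if the larger partner has the higher PPV, or to about 8.7 if it has the lower. If the sponsor prefers not to weight, publishing the partner-specific PPVs and phase 1 counts would still let a reader rebuild the overall figure.
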